Efficiency and Quality In Post- Surgical Pain Therapy After Discharge- EQUIPPED

NCT05221866

January 25, 2022

Methods

This trial was conducted at a Midwestern academic medical center and community hospital using a modified 2-by-2 randomized factorial design in which participants who underwent major inpatient surgery were randomly assigned to use a participant-facing consumer health informatics phone-based app with education versus an app for data collection only. Secondarily, a clinician-facing real-time opioid prescription decision support tool embedded into electronic health records was activated halfway through enrollment. The study design followed Pragmatic Explanatory Continuum Indicator Summary guidelines to maximize broad applicability and is reported according to Consolidated Standards of Reporting Trials Extension for Factorial Randomized Trials guidelines (Supplemental Digital Content 1).

Study design and participants

Participants were eligible for enrollment if they were 19-89 years old, had access to a smartphone, and had inpatient surgery requiring at least an overnight hospitalization with anticipated discharge to home. Individuals re-hospitalized within 30 days, pregnant, unable to read the English language, discharged to a post-acute care facility, with contraindications to opioids, acetaminophen, or nonsteroidal anti-inflammatory agents, or meeting the Agency for Healthcare Research and Quality (AHRQ) definition of long-term opioid therapy (opioid use on most days > 3 months) prior to surgery were excluded. All study data were deidentified.

Randomization and masking

Participants were randomized 1:1 to the consumer health informatics smartphone-based intervention app or a control app with only data collection. Permuted block randomization (pairs) was performed using a computer-generated code within a secure central online data management system, Research Electronic Data Capture (REDCap), which was used to store and manage all participant data. No randomization was instituted for the clinician-facing intervention; instead, the decision support tool was embedded into the electronic health record to facilitate optimized opioid prescription upon discharge based on recorded inpatient use. This was implemented after half of the participants were enrolled. The principal investigator, coinvestigators, clinical coordinating center staff, participants, and statisticians remained masked to treatment assignment until the database was locked for analysis.

Sample Size Justification

To estimate power and sample size for the primary outcome, self-reported cumulative opioid use in the four weeks after discharge, investigators combined data from previous observational studies on opiates taken at one week from discharge, where variability in opioid consumption is greatest, and summed across four weeks from discharge and then log-transformed values appropriately. Investigators utilized SAS Proc Power (version 15.2, SAS Institute Inc., Cary, NC, USA) software and specified significance level alpha = 0.05 two-tailed. Across decision support tool activation status and surgical subspecialties, 300 participants per app group provided 85% power to detect minimum effect sizes (ES) of 0.23 in opioids consumed at one week and of 0.245 in opioids consumed across four weeks. Data was similarly

combined for pain intensity scores from prior studies and could detect a minimum effect size of 0.244 in pain intensity t-score at week one following discharge. Within decision support tool type and across specialty (i.e., the three-way interaction among app, decision support tool, and time), 150 participants per group provided 85% power to detect minimum effect sizes of 0.35 in opioids consumed at one week, 0.35 in opioids consumed across four weeks, and 0.35 in pain intensity t-score at one week after discharge.

Procedures

Investigators primarily tested a participant-facing app to reduce opioid intake which was designed and implemented through a user-centered design approach. The intervention app provided education on elements of pain management that could be modified by patients, including: 1) post-operative pain expectations, 2) pharmacologic alternatives to opioids, 3) opioid safety and appropriate disposal, and 4) non-pharmacological therapy, such as meditation. The control app featured the same interface but only collected patient data. The app was deployed to research team members and pilot participants for beta testing before finalization.

Baseline information was obtained from the participant in-person during the index hospitalization. During this visit, patients familiarized themselves with the format, asked questions, and received explanations regarding the apps' functionality. Following discharge, a weekly notification was sent to the participant, reminding them to complete standardized surveys and custom questionnaires during the first four weeks following discharge, a time when most opioids are consumed and when patients have shown to report consumption accurately. The day of discharge was considered day 0. If no responses were obtained via the app, participants were followed up by telephone.

In addition to the participant-facing app intervention, a clinician-facing decision support tool was operationalized for the second half of the study period for participants not requiring opioids 24 hours prior to discharge. Previous work in three diverse samples of surgical procedures found that among available predictor variables that could be incorporated into an electronic decision support tool, 24-hour pre-discharge opioid intake was most strongly associated with patient-reported post-discharge opioid intake.

Outcomes

The primary outcome was self-reported cumulative oral morphine milligram equivalents (MME) in the first four weeks after discharge. The secondary outcomes were amount of opioid prescription at discharge, supplementary opioid prescriptions within four weeks after discharge, disposal of leftover opioids within four weeks of discharge, pain intensity scores during the four weeks after discharge, and pain interference scores during the four weeks after discharge. Non-opioid prescriptions within four weeks of discharge were an exploratory outcome. Pain intensity and interference were both quantified using the National Institutes of Health Patient-Reported Outcomes Measurement Information System (PROMIS®) four-item pain intensity scale at four weeks and the four-item scale pain interference score at four weeks. All PROMIS™ scores were analyzed as standardized T-scores (mean 50, standard deviation 10).

Independent variables included sociodemographic characteristics obtained from the electronic health record and from a questionnaire provided to participants during their hospitalization: age, sex, race, ethnicity, body mass index (kg m²-1), and insurance type. Health history variables were obtained via surveys and electronic health records as necessary and included history of substance use disorder, PROMIS™ Sleep Disturbance Score, Patient Health Questionnaire-(PHQ-8) score, pre-operative opioid use, preoperative benzodiazepine use, preoperative gabapentinoid use, and preoperative antidepressant use. Clinical characteristics included the primary surgical subspecialty for the requisite hospital stay, multiple procedures performed during admission, total in-hospital opioid intake, pain score at discharge, and length of hospital stay.

Adverse events were monitored. For this study, an adverse event was considered as one requiring more than two additional opioid prescriptions within two weeks of discharge and/or access of confidential information by a non-authorized person. We considered a serious adverse event as all-cause mortality and/or re-hospitalization for any reason.

Statistical analysis

Baseline balance on potential confounding characteristics was assessed using absolute standardized difference (ASD), calculated as the difference in means or proportions divided by the pooled standard deviation. A variable was considered imbalanced if the ASD was greater than 0.16.

For the primary analysis, the effect of the intervention app on self-reported cumulative opioid use in the four weeks after discharge was modeled by log-transforming the outcome variable and then fitting a linear regression model with the app treatment group as the covariate. The treatment effects were estimated as ratio of geometric means. A sensitivity analysis was conducted using quantile regression to test the robustness of results to outliers. A model was fit with an interaction between app and decision support tool groups to evaluate potential multiplicative effects between the groups. Analysis was on a modified intention-to-treat basis, excluding participants that did not engage with the intervention or answer survey questions. There were no partial responses to the opioid-related outcomes. Missing data from pain-related survey responses were imputed from the mixed effects model.

For the secondary analysis, the effect of the intervention app on opioids prescribed at discharge was modeled by log-transforming the outcome and fitting a linear regression model with the app treatment group as the covariate. The effect of the intervention app on supplementary opioid requirements in the four weeks after discharge, opioid disposal, and non- opioid prescriptions in the four weeks after discharge was evaluated using a logistic regression model. The effect of the app on pain intensity and interference t-scores was evaluated by fitting linear mixed models with fixed covariates for app treatment group and time (categorical), and random effects for participant identification code. No interim analyses were planned because the population studied was not considered high risk for adverse events, the interventions were generally considered not harmful and to prevent alpha dilution.

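### The decision support tool was switched on at mid-enrolment without randomization, so any tool contrast is an unadjusted before-after comparison and the app-by-tool interaction cannot be told apart from app-by-period

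*Combined protocol and SAP*

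**What the plan says.** The opening of Methods describes a "modified 2-by-2 randomized factorial design" and cites the CONSORT extension for factorial trials. The same paragraph applies random assignment to the app only and introduces the tool as secondary, noting that the "decision support tool embedded into electronic health records was activated halfway through enrollment".

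Randomization and masking is explicit about both factors. For the app: "Participants were randomized 1:1 to the consumer health informatics smartphone-based intervention app or a control app with only data collection", in permuted blocks of two. For the tool: "No randomization was instituted for the clinician-facing intervention", and on its timing, "This was implemented after half of the participants were enrolled".

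Procedures adds that the tool was "operationalized for the second half of the study period for participants not requiring opioids 24 hours prior to discharge".

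In Statistical analysis, the primary model for log cumulative opioid use has app group as its covariate. The tool enters in one sentence: "A model was fit with an interaction between app and decision support tool groups to evaluate potential multiplicative effects between the groups". No baseline covariate, hospital or calendar-time term is stated for that model. The same section sets an absolute standardized difference (ASD) of 0.16 as the flag for imbalance. It does not say which groups are compared or what follows from a flag.

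**The concern.** Tool-off and tool-on are the first and second halves of enrolment, with no concurrent control. Anything else that differed between the halves is carried into a tool contrast: case mix, the share of patients from each of the two hospitals, or general prescribing habits. Outcomes lists variables that could absorb part of this, such as subspecialty and preoperative opioid use, but the plan assigns none of them to the model that contains the tool.

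What is at stake is the secondary question: whether the tool reduces opioid use, and whether the app works differently alongside it. A reader who sees factorial results under a randomized label may give the tool result the same evidential weight as the app result.

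**Working it through.** **Inputs from the documents.** Sample Size Justification gives 300 per app group (600 in total), 150 per app group within tool status, two-sided alpha 0.05, 85% power, and detectable effects of 0.245 SD (four-week opioids, 300 per group) and 0.35 SD (150 per group). Activation at the midpoint splits the 600 into 300 per period and 150 per app-by-period cell.

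**Assumed inputs.** The documents give no drift between periods and no SD on the log scale. The drifts below are illustrations in SD units.

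**Step 1: reproduce the plan's power.** For two means with SD 1, power is about Φ(ES/SE − 1.96).
- 300 per group: SE = √(2/300) = 0.0816; 0.245/0.0816 = 3.00; power 85.1% (85.0% with the noncentral t). This agrees with the plan.
- 150 per group: SE = √(2/150) = 0.1155; 0.35/0.1155 = 3.03; power 85.8% (85.6% with the noncentral t). This agrees with the plan.

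**Step 2: tool contrast, no true tool effect.** Averaged over app arms, the contrast is period 2 minus period 1, so its bias equals the drift d. With SE = 0.0816, the rejection rate is Φ(d/SE − 1.96) + Φ(−d/SE − 1.96).

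| Assumed drift (SD) | d/SE | Declared a tool effect |
|---|---|---|
| 0.05 | 0.61 | 9% |
| 0.10 | 1.22 | 23% |
| 0.15 | 1.84 | 45% |
| 0.20 | 2.45 | 69% |
| 0.245 | 3.00 | 85% |

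On the natural scale, if the log SD were 1.0 to 1.5, a drift of 0.10 SD is a fall in geometric mean of 1 − exp(−0.10) = 10% to 1 − exp(−0.15) = 14%. The table is for the contrast averaged over app arms. If the interaction model is coded so that the tool coefficient refers to the control-app arm alone (150 v 150), the bias is the same and the rejection rate is lower.

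**Step 3: app-by-tool interaction.** The estimate is (app − control in period 2) − (app − control in period 1). A drift d common to both app arms adds d to both period-2 means and drops out. In 5,000 simulated trials per scenario, with shared drifts of 0, 0.10, 0.20 and 0.30 SD, the bias of the interaction was at most 0.004 in absolute value and rejection was 4.7% to 5.4%. The app effect averaged over periods was rejected 4.5% to 5.6% of the time.

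The term does respond if the app effect itself differs between halves for reasons other than the tool. With SE = √(4/150) = 0.1633:

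| Change in app effect (SD) | Change/SE | Declared an interaction |
|---|---|---|
| 0.10 | 0.61 | 9% |
| 0.20 | 1.22 | 23% |
| 0.30 | 1.84 | 45% |

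**Step 4: cost of a date term.** Scale enrolment time uniformly on 0 to 1, with a step at 0.5. The variance of the step is 1/4, the variance of time is 1/12, and their covariance is 3/8 − 1/4 = 1/8. The squared correlation is (1/64)/(1/48) = 0.75, so the variance of the tool contrast is multiplied by 1/(1 − 0.75) = 4 and its SE doubles.

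**The case against.** The strongest reply is that the plan hides nothing. The design is called modified, the tool is secondary, and the lack of randomization is stated outright. Statistical analysis frames its primary and secondary analyses as effects of the app and names no standalone test of the tool. The drift figures therefore describe a contrast that the plan does not single out, under drifts that the documents do not supply.

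Much of this stands. The rates are illustrations, and the tool contrast arises from the factorial framing and from the coefficients of the interaction model. But disclosing the design does not adjust the analysis or limit its interpretation, and a factorial report invites a tool estimate.

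A reader might also infer that the interaction is itself a before-after contrast. It is not: it is the difference between two randomized app effects, and shared drift on the log scale cancels. What remains open is attribution, because app-by-tool and app-by-period are one and the same term.

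Finally, the plan does not list every term of the interaction model. The accurate statement is that no adjustment is stated, not that adjustment is ruled out.

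**Conclusion.** The point holds in this form. Tool status equals enrolment period, so any tool contrast is a non-randomized before-after comparison with no stated adjustment, and its error rate depends on how far the two halves drifted apart. A drift as large as the plan's own four-week detectable effect would be declared a tool effect 85% of the time. The interaction is markedly less exposed, but a positive finding could not be credited to the tool rather than to the period.

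These sizes assume 600 analysed participants split evenly, a common SD on the log scale, and drifts chosen for illustration. The documents show no evidence that drift occurred.

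A reader might go further and conclude that the trial's main result is compromised. The documents do not support that: app allocation was randomized 1:1 in pairs, so both periods contribute balanced app arms, and shared drift leaves the app comparison's error rate at about 5%.

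**What to change.** - **Label.** Restrict the word randomized to the app factor, and describe the tool as a non-randomized before-after component.
- **Balance.** Report ASDs between tool periods as well as between app arms.
- **Tool contrast.** Adjust for pre-operative variables already collected, such as age, subspecialty and preoperative opioid use, and for hospital if it is recorded. Use in-hospital opioid intake, discharge pain and length of stay only in a sensitivity analysis of the tool contrast. Patients were shown the apps during the hospital stay and the timing of randomization is not stated, so these variables may post-date app assignment.
- **Date sensitivity analysis.** Add an enrolment-date term to the tool contrast. It should not be the main model, given the fourfold variance.
- **Interaction.** As sensitivity analyses, add app-by-date or app-by-covariate terms. Main-effect adjustment alone cannot separate app-by-tool from app-by-period.
- **Primary model.** Leave the app model as planned.
- **Reporting.** Present tool and interaction results as associations.

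The cost is a change of SAP wording and some extra model terms, almost all from variables already collected. The downside is a weaker claim for the tool and imprecise date-adjusted estimates.

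### Sample size section: the 0.35 effect size is a within-status app effect, not the three-way interaction it is called, and 0.23 at one week has about 80% power, not 85%

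*Combined protocol and SAP*

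**What the plan says.** The Sample Size Justification works at two-sided alpha 0.05 and gives two sets of minimum detectable effect sizes.

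- **Whole trial, by app.** "300 participants per app group provided 85% power to detect minimum effect sizes (ES) of 0.23 in opioids consumed at one week". The same sentence gives 0.245 for opioids over four weeks, and the next gives 0.244 for pain intensity at week one.
- **Smaller groups.** "Within decision support tool type and across specialty (i.e., the three-way interaction among app, decision support tool, and time), 150 participants per group" are said to have "provided 85% power to detect minimum effect sizes of 0.35 in opioids consumed at one week, 0.35 in opioids consumed across four weeks". The sentence closes by giving the same value, 0.35, for week-one pain intensity.

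The 150 follows from the design. Allocation to the apps is 1:1, and of the decision support tool the Randomization and masking section says "This was implemented after half of the participants were enrolled". That gives four app-by-period cells of 150.

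Under Outcomes, "The primary outcome was self-reported cumulative oral morphine milligram equivalents (MME) in the first four weeks after discharge". One-week opioid use is not a listed outcome.

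Under Statistical analysis, the primary model for log opioid use has app group as its only covariate. In addition, "A model was fit with an interaction between app and decision support tool groups". The pain models have app and categorical time as fixed effects and a random participant effect. They have no tool term and no interaction.

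**The concern.** There are two separate problems in the same paragraph.

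**Label.** The sentence opens by describing a comparison inside one decision-support status, then glosses it as a three-way interaction of app, tool and time. These are different estimands with different standard errors. Each 0.35 is attached to one value per participant (one-week opioids, the four-week total, one-week pain), and the planned models have no three-way term. A reader would conclude that an interaction was powered at 85% and could over-read a null app-by-tool result, when no power is stated for that test.

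**One-week figure.** For the same two-group comparison with the same n, alpha and power, the 85% minimum in standardised units is the same for every outcome. The plan gives 0.245 and 0.244 for two outcomes but 0.23 for the third.

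**Working it through.** **Inputs (Sample Size Justification):** two-sided alpha 0.05; power 85%; 300 per app group; 150 per group within tool status; effect sizes 0.23, 0.245, 0.244 and 0.35. The plan does not define effect size; a standardised mean difference (SD = 1) is assumed and tested first against the plan's own figures.

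**Formulas.** For two groups of n, SE = √(2/n). To a normal approximation, power = Φ(d/SE − 1.960) and the 85% minimum is (1.960 + 1.036) × SE. The figures below use the exact noncentral t unless marked otherwise.

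**Step 1. Reproduce the plan.**

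| Comparison | n per group | Stated effect size | Stated power | Computed power | Computed 85% minimum |
|---|---|---|---|---|---|
| Four-week opioids | 300 | 0.245 | 85% | 85.0% | 0.245 |
| Week-one pain | 300 | 0.244 | 85% | 84.7% | 0.245 |
| Any outcome, two apps within one tool status | 150 | 0.35 | 85% | 85.6% | 0.347 |
| One-week opioids | 300 | 0.23 | 85% | **80.3%** | 0.245 |

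Every figure but 0.23 reproduces on this reading. For 0.23 by the normal formula: SE = √(2/300) = 0.0816, 0.23/0.0816 = 2.817, and Φ(2.817 − 1.960) = 0.804.

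**Step 2. Can rounding or sidedness explain 0.23?** Values from 0.225 to 0.235 give 78.6% to 82.0%. A one-sided test gives 87.9% (normal). Neither is 85%. The 80% minimum with 300 per group is 0.229, so 0.23 is what an 80% calculation would produce, but the plan does not show its origin. At 85% power, 0.23 needs 340.4, so 341 per group.

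**Step 3. Check the plan against itself.** If effect size is proportional to the standard error, with the same SD and model at both sample sizes, going from 300 to 150 per group multiplies an 85% minimum by 0.3471/0.2450 = 1.416, whatever that SD is. The stated pairs, allowing for rounding, give:

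- four-week opioids: 0.345/0.2455 to 0.355/0.2445 = 1.405 to 1.452, which contains 1.416;
- pain: 0.345/0.2445 to 0.355/0.2435 = 1.411 to 1.458, which contains 1.416;
- one-week opioids: 0.345/0.235 to 0.355/0.225 = 1.468 to 1.578, which does not.

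If 0.23 were right with 300, the figure with 150 would be 1.416 × (0.225 to 0.235) = 0.319 to 0.333, not 0.35.

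**Step 4. What 0.35 would mean as an interaction.**

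- *App by tool, full difference between the two app effects, four cells of 150:* SE = √(4/150) = 0.163 SD. Power at 0.35 is 57%, and the 85% minimum is 0.490.
- *Same test coded as half that difference:* SE = 0.082, and the 85% minimum is 0.245. Neither coding gives 0.35 at 85%.
- *Three-way, with a change between two times (normal):* the variance is multiplied by 2(1 − ρ), where ρ is the within-person correlation. Power at 0.35 is 33% at ρ = 0, 57% at ρ = 0.5 and 79% at ρ = 0.7. It reaches 85% only near ρ = 0.74, and the plan gives no correlation.

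**Step 5. Sensitivity to the definition of tool group.** Equal cells are the best case for 600 participants. Procedures says the tool was "operationalized for the second half of the study period for participants not requiring opioids 24 hours prior to discharge". If tool group meant exposure rather than enrolment period, a fraction f of the second half being exposed gives cells of 150f, 150f, 300 − 150f and 300 − 150f. No rate is given. For assumed f of 0.75, 0.50 and 0.25, power at 0.35 is 54%, 46% and 29%, and the 85% minimum is 0.51, 0.57 and 0.74.

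**The case against.** The arithmetic is not in dispute; the objections concern certainty and weight.

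- **Effect size is undefined and the software inputs are not shown.** This stands as a caveat. It does not remove the inconsistency, because the natural reading reproduces the other stated figures.
- **The ratio check assumes an effect size linear in the standard error.** This is correct. Since the outcome is log-transformed and reported as a ratio of geometric means, effect size might mean ratio minus 1. Then 0.225 to 0.235 scales to 0.333 to 0.348, which overlaps values rounding to 0.35. But the four-week pair then fails: 0.245 would scale to about 0.364. No single reading makes the whole paragraph consistent.
- **Covariate adjustment could give 0.23.** An R² of 1 − (0.23/0.2446)² ≈ 0.12 would do it. None is stated, and the primary model has only app group.
- **The label is loose wording.** The right meaning is in the opening words, and in a repeated-measures model a week-one app effect within one tool status can be taken as a contrast from an app-by-tool-by-time model. That is fair for the two week-one quantities, though not for the four-week total. A simple effect drawn from such a model is still not its interaction, and no such model is planned.
- **The interaction figures do not correct anything stated.** Agreed. They show what the mislabelled number is not and fill a gap. The exposure rates are assumptions and can be left out.

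**Conclusion.** Both points hold, and both are minor. The 0.35 figure is the minimum app effect within one decision-support status (85.6% power with 150 per group). It is not a three-way interaction, and the app-by-tool interaction actually fitted has no stated power. The one-week figure of 0.23 has 80.3% power with 300 per group, 4.7 percentage points below the 85% claimed.

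The conclusion on 0.23 rests on reading effect size as a standardised mean difference in an unadjusted two-group comparison. The label point needs less: it follows from the sentence itself and from the models listed under Statistical analysis. The 0.49 SD for the interaction also assumes four equal cells and the full-difference definition.

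The consequence is limited. The power claim for the primary outcome is correct, the primary analysis does not depend on the interaction, and one-week opioid use is not a listed outcome.

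**What to change.** In the Sample Size Justification:

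1. Define effect size.
2. Describe 0.35 as the minimum app effect within decision-support status, and delete the parenthesis about the three-way interaction.
3. For one-week opioids, change 0.23 to 0.245, or restate it as 80% power, or document the assumption that produced it.

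Useful additions, not needed to correct the errors: state the minimum detectable app-by-tool interaction (about 0.49 SD at 85% power) with its definition and equal-cell assumption; say whether tool group means enrolment period or exposure; and report the interaction with its 95% confidence interval.

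The cost is wording only, with no extra participants and no change to the primary analysis or its stated power.

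### The app-by-tool interaction is not restricted to the participants for whom the decision support tool operated, so any interaction is diluted by an eligible share that the plan does not state

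*Combined protocol and SAP*

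**What the plan says.** Two sections describe the tool's reach differently. Randomization and masking says it was built into the health record "to facilitate optimized opioid prescription upon discharge based on recorded inpatient use", with no subgroup named, and gives its timing: "This was implemented after half of the participants were enrolled". It was not randomized. Procedures is narrower: the tool was put into use in the second half of the study "for participants not requiring opioids 24 hours prior to discharge".

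The tool enters the analysis in one place. Under Statistical analysis, "A model was fit with an interaction between app and decision support tool groups". Those groups are not defined there or elsewhere, and the model carries no eligibility restriction. The modified intention-to-treat exclusions concern non-engagement and unanswered surveys, not tool eligibility.

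Sample Size Justification states that "150 participants per group provided 85% power to detect minimum effect sizes of 0.35 in opioids consumed at one week", and labels this a three-way interaction of app, tool and time. With 300 per app group, 150 is half of each app group, so everyone is counted by period.

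The share of participants meeting the 24-hour criterion is not given. The variables listed under Outcomes include total in-hospital opioid intake but not intake in the 24 hours before discharge.

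**The concern.** If Procedures is right about the tool's reach, the second-half group mixes participants the tool could act on with participants it could not. Analysing both as tool-exposed averages the interaction over the whole group. If the tool has no effect outside its criterion, the expected interaction is q times the interaction among eligible participants.

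The trial is presented as a modified 2-by-2 factorial, so readers will look for the interaction result. With q unstated, a null interaction could mean that app and tool do not modify each other, or that too few participants were exposed to the tool. Because 24-hour intake is not a listed variable, the planned data set might not allow the two to be separated afterwards.

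**Working it through.** **Inputs.** From Sample Size Justification: 300 per app group, 150 per app-by-period cell, and "specified significance level alpha = 0.05 two-tailed" (critical value 1.96). Assumptions: SD 1 (the stated effects are read as standardized), equal SDs in all cells, all 600 analysed, the same q in every cell, and no tool effect in participants outside the criterion. The plan does not give q, so 25%, 50% and 75% are shown.

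**Step 1. Reproduce the stated figure.** Two groups of 150, effect 0.35:

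- SE = sqrt(2/150) = 0.1155; 0.35/0.1155 = 3.03
- power = Φ(3.03 − 1.96) = 86%

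This matches the stated 85%. The figure is therefore app versus control within one tool period.

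**Step 2. The interaction with all 600, before dilution.** A difference of differences over four cells of 150:

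- SE = sqrt(4/150) = 0.163
- effect of 0.35: 0.35/0.163 = 2.14, power 57%
- effect detectable with 85% power: (1.960 + 1.036) × 0.163 = 0.49

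**Step 3. Everyone analysed.** An interaction of 0.49 among eligible participants becomes 0.49q, with SE still 0.163.

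**Step 4. Eligible participants only, in both periods.** The effect stays at 0.49, cell size is 150q, and SE = sqrt(4/(150q)).

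| q | Diluted effect | Power, all 600 | Cell size, eligible | SE, eligible | Power, eligible only |
|---|---|---|---|---|---|
| 25% | 0.1225 | 12% | 37.5 | 0.327 | 32% |
| 50% | 0.245 | 32% | 75 | 0.231 | 56% |
| 75% | 0.3675 | 61% | 112.5 | 0.189 | 74% |

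Example at q = 50%: in everyone, 0.245/0.163 = 1.50, power 32%; in eligible participants, 0.49/0.231 = 2.12, power 56%.

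**Step 5. General form.** The eligible-participant interaction detectable with 85% power is 0.49/q in everyone and 0.49/sqrt(q) in eligible participants only:

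| q | All 600 | Eligible only |
|---|---|---|
| 25% | 1.96 | 0.98 |
| 50% | 0.98 | 0.69 |
| 75% | 0.65 | 0.57 |

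Restriction costs a factor 1/sqrt(q) in SE and avoids a loss of q in signal, so on these assumptions it has more power at every q below 100%.

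**The case against.** **The wording may not conflict.** A tool driven by recorded inpatient use could be triggered by the absence of use in the last 24 hours, so one section may be general and the other specific. That is plausible, but the document should say so. If the narrower description holds, the dilution follows.

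**The all-participant estimate has its own meaning.** The plan declares a pragmatic design and treats the tool as secondary. How the app effect changes once the tool is switched on for a whole service is a legitimate question. This stands, and is why the restricted estimate belongs beside the all-participant interaction and should not replace it.

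**The restricted estimate has weaknesses.** It is still a before/after comparison, and it conditions on opioid use recorded late in the stay. Participants were introduced to the app during that stay, so the flag follows app allocation. Both limits stand and should be stated.

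A reader might also infer several stronger points that the documents do not support:

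- *That a tool-effect analysis and its power are diluted.* No stand-alone tool analysis is listed and no tool power is given. The tool enters only through the interaction model.
- *That the stated 85% at 0.35 assumes full tool exposure.* Step 1 shows an app comparison within one period, whose arithmetic does not depend on the tool's reach. Its fault is being labelled an interaction.
- *That the tool acts where there is least room for an effect.* Procedures links 24-hour intake to later consumption. It does not show that discharge prescriptions, a secondary outcome, were already small.
- *That ineligible participants could serve as a concurrent comparison and remove calendar drift at no cost.* Drift cancels only if it is equal in both groups. The SE becomes 0.163/sqrt(q(1−q)), so power for the 0.49 interaction is about 26%, 32% and 26% at q = 25%, 50% and 75%. That is no better than the all-participant analysis at 50% and well below its 61% at 75%.

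**Conclusion.** The concern holds for the app-by-tool interaction, conditional on the description in Procedures. That the interaction uses everyone in the period is inferred from 150 = 600/4 and the absence of any restriction, since the tool groups are undefined.

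The interaction is then attenuated by q, and the sample needed for a given eligible-participant interaction rises by 1/q² (fourfold at q = 50%). The power figures rest on equal SDs, no tool effect outside the criterion and an assumed range for q. If prescribers also changed practice for participants outside the criterion, the dilution would differ.

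A reader might carry the problem over to the primary result. That would be wrong: the primary model compares randomized app groups in all participants and does not depend on how far the tool reached. This is a should-fix point about a secondary analysis.

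**What to change.** 1. Reconcile Procedures with Randomization and masking on which participants the tool operated for, and define the tool groups in Statistical analysis.
2. Derive a flag from the health record for no opioid requirement in the 24 hours before discharge, in both periods, and report its share by period and app group.
3. Keep the all-participant interaction and add an app-by-tool estimate among flagged participants in both periods.
4. Restate interaction power as a difference of differences for the expected flagged number, with a detectable effect at 85% power of about 0.49/sqrt(q) SD. Label the existing 0.35 figure as app versus control within a tool period.
5. State that the flagged estimate is a before/after comparison and that the flag is set after app allocation.

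The cost is one derived variable and one extra model, with no change to recruitment, randomization or the primary analysis. The flagged subgroup will be small if q is low, and its estimate should then be presented as imprecise.
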